## 7. SUBJECT DISPOSITION

For all subjects randomized, subject disposition will be summarized. Subject disposition includes the number of subjects in the following categories:

- ITT Population
- Safety Population

Reasons for treatment termination will be collected on the CRF and will be summarized for all randomized subjects with the following categories:

- Adverse events
- Disease progression
- Withdrew consent
- Death
- Lost to follow-up
- Protocol violation
- Other

A separate listing will be provided for subjects who did not receive at least one dose of study drug.

## **8. DEMOGRAPHICS AND BASELINE CHARACTERISTICS**

Subjects' age, weight, and other continuous demographic and baseline variables including disease characteristics and prior treatments (Number of prior regimens Purine-analog refractory in any prior treatment line, percentage of subjects that received purine-analog treatment, bendamustine treatment or both in a line prior to study entry) will be summarized using descriptive statistics (e.g., mean, standard deviation, median, minimum and maximum), while the response to previous CLL treatment, race and other categorical variables will be summarized with frequency tabulations for each treatment arm separately and pooled over all treatment arms. Cytogenetic abnormalities will be identified and summarized by treatment arm.

Summaries for the demographics and baseline characteristics will be provided for the ITT population and safety population separately. Individual subject listings will be provided.

Medical history data will be summarized using frequency tabulations for each treatment arm by system organ class and preferred term separately and pooled over all arms using the safety population.

## 9. DRUG EXPOSURE

The following measures of drug exposure will be analyzed for all three treatment arms.

### Treatment Duration

The first dose date of lenalidomide is considered the start date of the study treatment. For each cycle, the lenalidomide start date will be considered the cycle start date and the day before that (after the 1st cycle) will be considered the end day of the previous cycle. The end date of the last cycle will be calculated as the start date of last treatment cycle plus 27 days, unless subject discontinues study or dies before the end of the last cycle, in which case the end date of the last cycle will be the treatment discontinuation date or the death date.

For each treatment arm, the treatment duration will also be calculated, and defined as:

$$[(\text{The end of the last cycle of the study drug}) - (\text{the first dose date of the study drug}) + 1]$$

### Cumulative Dose

Cumulative dose will be calculated for each lenalidomide arm. The cumulative dose is defined as the sum of all doses taken across the treatment period (in milligrams).

### Dose Exposure

Dose exposure will be calculated for each lenalidomide arm. Dose exposure is defined as the total number of days on the study drug during the treatment phase (excluding the periods of dose interruptions per protocol).

### Average Daily Dose

Average dose will be calculated for each lenalidomide arm. Average daily dose is defined as the cumulative dose divided by dose exposure (mg/day).

### Dose Intensity

Dose intensity will be calculated for each lenalidomide arm. Dose intensity is defined as the cumulative dose divided by treatment duration (mg/day).

Descriptive statistics of treatment duration, cumulative dose, dose exposure, average daily dose, and dose intensity, will be presented by treatment arm. In addition, descriptive statistics for treatment duration in weeks and associated frequency tables, as well as the number of cycles on study drug, will be presented by treatment arm.

The dosing statistics as described above may be presented by cycle for each treatment arm.

Dose reduction/interruption and re-escalation will be summarized. Summaries will include subjects who have at least one dose reduction/interruption due to AE, time to first dose reduction/interruption due to AE. Additional descriptive statistics will include, subjects who have a second dose reduction/interruption due to AE, duration of first and second dose reduction/interruption due to AE and interval between first and second dose reduction/interruption due to AE. The dose reduction/interruption and re-escalation may be presented by cycle for each arm.

## 10. PRIOR/CONCOMITANT MEDICATIONS

Prior medications (prescription and non-prescription) are defined as medications that were started before the start of the study treatment (whether or not ended before the start of the study treatment). Concomitant medications are defined as non-study medications that are started after the start of the first dose of the study drug and taken through the last dose of study drug.

All concomitant medication usage and procedures documented during the study period will be summarized in frequency tabulations for each treatment arm separately and pooled over all arms using the safety population. The Anatomical Therapeutic Chemical (ATC) coding scheme of the World Health Organization (WHO) will be used to group medications into relevant categories for these tabulations.

Listings of prior/concomitant medications by subject will be provided.

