9.2. Subject Exclusion Criteria

Subjects must not meet any of the following exclusion criteria to be eligible for enrollment into the study:

- 1. Any serious medical condition, laboratory abnormality, or psychiatric illness that would prevent the subject from signing the informed consent form
- 2. Active infections requiring systemic antibiotics
- 3. Systemic treatment for B-cell CLL within 28 days of initiation of lenalidomide treatment
- 4. Alemtuzumab therapy within 60 days of initiating lenalidomide treatment
- 5. (removed in protocol amendment #3)
- 6. Prior therapy with lenalidomide
- 7. History of grade 4 rash due to prior thalidomide treatment
- 8. Planned autologous or allogeneic bone marrow transplantation

- 9. Pregnant or lactating females
- 10. Central nervous system (CNS) involvement as documented by spinal fluid cytology or imaging. Subjects who have signs or symptoms suggestive of leukemic meningitis or a history of leukemic meningitis must have a lumbar puncture procedure performed within two weeks prior to initiating study drug
- 11. Prior history of malignancies, other than CLL, unless the subject has been free of the disease for ≥5 years. Exceptions include the following:
 - Basal cell carcinoma of the skin
 - Squamous cell carcinoma of the skin
 - Carcinoma in situ of the cervix
 - Carcinoma in situ of the breast
 - Carcinoma in situ of the bladder
 - Incidental histologic finding of prostate cancer (TNM stage of T1a or T1b)
- 12. History of renal failure requiring dialysis
- 13. Known Human Immunodeficiency Virus (HIV), Hepatitis B Virus (HBV) and/or Hepatitis C Virus (HCV) infection
- 14. Evidence of TLS per the Cairo-Bishop definition of laboratory TLS (subjects may be enrolled upon correction of electrolyte abnormalities)
- 15. Any of the following laboratory abnormalities:
 - Calculated (method of Cockroft-Gault) creatinine clearance of <60 mL/min (creatinine clearance may also be obtained by the 24-hour collection method at the investigator's discretion)
 - Absolute neutrophil count (ANC) $\leq 1,000/\mu L (1.0 \text{ X } 10^9/L)$
 - $-\quad Platelet\ count \leq 50,\!000/\mu L\ (50\ X\ 10^9/L)$
 - Serum aspartate aminotransferase (AST)/serum glutamic-oxaloacetic transaminase (SGOT) or alanine transaminase (ALT)/serum glutamate pyruvate transaminase (SGPT) > 3.0 x upper limit of normal (ULN)
 - Serum total bilirubin > 1.5 x ULN
- 16. Uncontrolled hyperthyroidism or hypothyroidism
- 17. Venous thromboembolism within 12 months

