10.4. Prior/Concomitant Medications

All medications (prescription and non-prescription), treatments and therapies taken from 28 days prior to Cycle 1 Day 1 through the last dose of study drug, must be recorded on the eCRF.

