10.4.1. Prophylaxis and/or Treatment for TLS, TFR, Neutropenia, and Thromboembolic Events

10.4.1.1. Tumor Lysis Syndrome (TLS) Prophylaxis

TLS prophylaxis, comprising of oral hydration and allopurinol 300 mg/day will be initiated at least 3 days prior to starting study drug and for a minimum of the first 3 treatment cycles. For subjects with known allergy to allopurinol prior to study initiation or for those who develop an allergy during the course of study, the medical monitor should be contacted. To maintain fluid intake, subjects must be instructed to drink 8 to 10 eight ounce (240 mL) glasses of water each day for the first 14 days of each cycle during the dose escalation period. Hydration levels should be adjusted according to age and clinical status, and lowered if the subject's cardiovascular status indicates the possibility of volume overload.

Subjects will be monitored for TLS as follows:

- On Day 2 and 4 and then weekly (Days 8, 15, 22) for cycle 1 and the first cycle of each dose escalation
- On Day 1, 8 and 15 of cycle 2 (if not dose escalated)
- At least every 28 days thereafter and as clinically indicated.

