10.4.1.4. Infection Prophylaxis

Prophylactic antibiotics should be considered in subjects with neutropenia. In addition, subjects who were on prophylactic treatment for infection while on alemtuzumab therapy should continue prophylactic treatment for at least 6 months following the discontinuation of alemtuzumab therapy and can be enrolled into the study while continuing prophylactic therapy.

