15.7. Concomitant Therapy

All concomitant treatment usage documented during the study period will be summarized in frequency tabulations for each treatment group separately. The Anatomical Therapeutical Chemical (ATC) coding scheme of the World Health Organization (WHO) will be used to group medications into relevant categories for these tabulations.

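### SAP 10 leaves out of the concomitant-medication table every drug started before the first dose, including the required allopurinol

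*SAP*

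**What the plan says.** SAP 10 has two classes. Prior medications are "medications that were started before the start of the study treatment (whether or not ended before the start of the study treatment"), so a drug that continues into treatment stays in the prior class. For the other class it says: "Concomitant medications are defined as non-study medications that are started after the start of the first dose of the study drug". The same sentence adds that such a drug is taken through the last dose of study drug.

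Only the second class is tabulated: "All concomitant medication usage and procedures documented during the study period will be summarized in frequency tabulations for each treatment arm separately". The tables are also pooled over arms and use the safety population. Prior drugs appear only in by-subject listings.

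Protocol 15.7 makes almost the same promise, but with no condition on the start date: "All concomitant treatment usage documented during the study period will be summarized in frequency tabulations for each treatment group separately". The synopsis, under Safety Analysis, likewise has concomitant medications tabulated by arm for the period on therapy. Protocol 10.4 makes sure the data exist, since all medications "taken from 28 days prior to Cycle 1 Day 1 through the last dose of study drug, must be recorded on the eCRF".

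Three supportive treatments matter here:

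- **Allopurinol with hydration** (Protocol 10.4.1.1) "will be initiated at least 3 days prior to starting study drug and for a minimum of the first 3 treatment cycles".
- **Infection prophylaxis** (Protocol 10.4.1.4): subjects already on it because of alemtuzumab are to continue for at least 6 months after alemtuzumab stops, and "can be enrolled into the study while continuing prophylactic therapy".
- **Anti-thrombotic prophylaxis** (Protocol 10.4.1.5) is intended for all subjects during study treatment. No start day is given.

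**The concern.** A concomitant-medication table should show what subjects were taking alongside study drug. SAP 10 shows what they began after the first dose, which is a different set. The drugs lost are those the protocol requires, or expects to continue, at the start of treatment.

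Safety is the primary endpoint, and the synopsis names tumor lysis syndrome (TLS) and thrombosis among the clinically important events to be summarised. A reader of those summaries will turn to the medication table to see how many subjects in each arm had prophylaxis. For allopurinol, the only subjects who could appear are those who began it after the first dose, contrary to the schedule. A near-empty row would then suggest that prophylaxis was hardly used, when it could equally mean that the schedule was followed.

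**Working it through.** The plan gives no figure to reproduce. The check applies the SAP 10 rule to the drugs that the protocol describes and compares the result with what Protocol 15.7 promises.

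**1. The classification rule.** Count the first-dose date as Day 1. Under SAP 10, a start before Day 1 is prior and goes to a listing only. A start after Day 1 can be concomitant and enter the table. A start on Day 1 is addressed by neither phrase.

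| Drug and timing | SAP 10 class | Taken on treatment? | Tabulated? |
|---|---|---|---|
| Allopurinol, started at least 3 days before and continued through cycle 3 | Prior | Yes | No |
| Infection prophylaxis continued from alemtuzumab | Prior | Yes | No |
| Anti-thrombotic already being taken before Day 1 | Prior | Yes | No |
| Any drug started on Day 1 | Not clearly classed | Yes | Unclear |
| Growth factor on Days 20 to 25 only, as an example | Meets the start condition; fails the end condition if read literally | Yes | Unclear |

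**2. Allopurinol: how much of the course is on treatment.** Inputs from Protocol 10.4.1.1: at least 3 days before study drug and at least 3 cycles. Cycles are 28 days.

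- Shortest compliant course = 3 + 3 × 28 = 87 days.
- Part on treatment = 3 × 28 = 84 days.
- Share = 84 / 87 = 96.6%.

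An earlier start lowers the share, but the 84 days on treatment remain.

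**3. Infection prophylaxis: an illustration for one subject.** Protocol 9.2 excludes "Alemtuzumab therapy within 60 days of initiating lenalidomide treatment". SAP 6.5.3 converts at 30.4 days per month.

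- Minimum course = 6 × 30.4 = 182.4 days.
- Remaining for a subject who enters at the 60-day limit = 182.4 − 60 = 122.4 days.

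So up to about 122 days of the minimum course fall on study and go untabulated. A subject entering later has less remaining. The documents do not say how many subjects this describes.

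**4. The end condition.** Read literally, the requirement of use through the last dose also removes drugs started on study and stopped before the last dose, such as a short course of antibiotics. That is unlikely to be intended, but it is what the sentence says.

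**5. The first-dose date.** SAP 6.5.3 imputes partial start dates partly to separate prior from concomitant medication. A start known only to the month, in the month of the first dose, is set to the first-dose date. So is a start known only to the year, in that year. Both land on the one date that SAP 10 does not address.

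**6. Against the protocol.** The tabulation sentences in SAP 10 and Protocol 15.7 are nearly the same, so the SAP evidently means to deliver the protocol's table. The definition placed before that sentence prevents it.

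**The case against.** The strongest reply is that nothing is lost. Every drug is on the eCRF and in a by-subject listing, Protocol 15.7 does not itself define concomitant, and neither document plans an analysis linking prophylaxis to TLS or thrombosis. All of this is true, and it keeps the point minor. It does not remove it. A drug taken daily for three cycles is treatment used during the study period on any ordinary reading, and a listing is not the promised table.

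A second reply is that the sentence is loose drafting and that programmers would apply the usual meaning. That is plausible for the end condition and for Day 1 starts, where the evident intent is to count the drug, so those two are drafting gaps. It does not work for drugs begun earlier: the remark in SAP 10 that it does not matter whether they ended shows that continuing drugs were considered and placed in the prior class.

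Three stronger readings are tempting, and the documents do not support them:

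- **That the size of the allopurinol row can be predicted.** No compliance figures are given. The SAP reports 104 enrolled, but the table uses the safety population. The end condition could also remove late starters who stopped before the last dose.
- **That all anti-thrombotic prophylaxis disappears.** Protocol 10.4.1.5 gives no start day, so this applies only to subjects who began before the first dose.
- **That TLS reporting itself is damaged.** SAP 12.1 analyses TLS by Cairo-Bishop grade, takes severity from the CRF, counts treatment-emergent events to 30 days after the last dose and summarises events of interest by cycle. The medication definition touches none of this.

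**Conclusion.** The point holds and is minor. As written, SAP 10 leaves allopurinol out of the concomitant-medication table for every subject who starts it as required, although at least 84 days of use fall on treatment. This assumes only that SAP 10 is programmed as worded and that the subject completes the three required cycles. Carried-over infection prophylaxis, and anti-thrombotics begun before the first dose, are left out by the same rule, in unknown numbers. The end condition and the unaddressed first-dose date are smaller gaps in the same definition.

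A reader might infer that the comparison between arms is biased. The documents do not show that: the same rule applies to all three arms, and the effect on the comparison could be zero. What is wrong is a descriptive table that would misstate use of required prophylaxis and would not match Protocol 15.7 or the synopsis.

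**What to change.** Replace the definition of concomitant medication in SAP 10 with:

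*Concomitant medication is any non-study medication taken at any time on or after the first dose through the last dose of study drug, whatever its start or stop date. A drug started earlier and continuing is both prior and concomitant. A drug not known to have stopped before the first dose is counted as concomitant.*

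This restores the table in Protocol 15.7, removes the end condition and settles starts on the first-dose date. SAP 6.5.3 can stay as it is, because a start imputed to that date then falls inside the class.

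The cost is a short change of text and of one derivation, using data already collected from 28 days before Cycle 1 Day 1. The downside is a longer table, because long-term medication enters it, with some drugs in both classes. A footnote should say so. No change to treatment or prophylaxis is involved.

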## 11. EFFICACY ANALYSIS

Efficacy analysis will be performed on the intent-to-treat population. Adjudicated response as will be used for these analyses. Sensitivity analysis will be done based on investigator's assessment.

Subgroup analysis might be done by duration of treatment (completed 3 cycles vs. withdraw treatment by Cycle 4 Day 1).

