- e. All male and FCBP subjects must be counseled about pregnancy precautions and risks of fetal exposure as detailed in Appendix 21.9 Pregnancy Prevention Risk Minimization Plans.
- f. Physical examination of the lymph nodes, spleen and liver will be performed at screening, Study Day 1 and every 28 days thereafter and at the treatment discontinuation visit. Lymph node evaluation will record the bi-dimensional diameter of the largest palpable nodes in each of the following sites: cervical, axillary, supraclavicular, inguinal and femoral. The size of the liver and spleen will be assessed by palpation and recorded.
- g. Vital signs include: temperature, pulse, blood pressure, weight and height (height to be measured during screening only).
- h. CT scans of the neck, chest, abdomen and pelvis to assess lymphadenopathies will be performed during screening and at the PR and CR/CRi confirmation visits (≥8 weeks ≤ 12 weeks after all clinical and laboratory response criteria have been met for PR or CR/CRi) and for all subjects, except those who discontinue due to PDs, at the treatment discontinuation visit. At screening, if medically justified, the possibility of not repeating the CT Scan when previously performed within 56 days of randomization will be evaluated by the Celgene Medical Monitor on a case by case basis. Those subjects whose response was down-graded based on the CT scan interpretation at the PR or CR/CRi confirmation visit will have the CT scan repeated 4 months later at the location where remaining disease has been documented as long as clinical and laboratory response remains present to try to document further improvement.
- i. ECG will be performed and interpreted locally. After the screening ECG, the next ECG will be done at Cycle 3 Day 1, and then every 12 weeks while on study drug, and at treatment discontinuation.

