If a study drug interruption has lasted for 5 weeks (35 days), the investigator should contact the medical monitor to discuss whether the subject should be continued on the study.

Table 6: Dose Reduction Steps for Lenalidomide

	Lenalidomide dose (oral administration)			
Dose level	Treatment Arm 1 5 mg starting dose arm	Treatment Arm 2 10 mg starting dose arm	Treatment Arm 3 15 mg starting dose arm	Schedule
Dose level +4 a	25 mg daily	25 mg daily ^b	25 mg daily ^c	28 days
Dose level +3 a	20 mg daily	25 mg daily	25 mg daily ^c	28 days
Dose level +2 a	15 mg daily	20 mg daily	25 mg daily	28 days
Dose level +1 ^a	10 mg daily	15 mg daily	20 mg daily	28 days
Dose level 0	5 mg daily	10 mg daily	15 mg daily	28 days
Dose level -1	2.5 mg daily	5 mg daily	10 mg daily	28 days
Dose level -2	2.5 mg every other day	2.5 mg daily	5 mg daily	28 days
Dose level -3 ^d	2.5 mg 2x per week	2.5 mg every other day	2.5 mg daily	28 days
Dose level -4 ^d	Not Applicable	2.5 mg 2x per week	2.5 mg every other day	28 days

- a. If a subject is at Dose Levels +1, +2, +3 or +4, a maximum of 5 consecutive dose reductions are allowed. If a 6th consecutive dose reduction is required, the subject will be discontinued from the study.
- b. For the 10 mg starting dose arm, if a dose reduction is required at Dose Level +4 (25 mg daily), the subject will be dose reduced directly to Dose level +2 (20 mg daily). This will be counted as one dose reduction.
- c. For the 15 mg starting dose arm, if a dose reduction is required at Dose Level +3 (25 mg daily) or Dose Level +4 (25 mg daily), the subject will be dose reduced directly to Dose level +1 (20 mg daily). This will be counted as one dose reduction.
- d. If a dose reduction is required at Dose Level -4 (or at dose level -3 in the 5 mg starting dose arm) subject will be discontinued from the study.

Site staff must contact Celgene to obtain new study drug bottle for a patient. If the treatment has been withheld and the next cycle is delayed beyond 29 days after Day 1 of the prior cycle, then Day 1 of the next cycle will be defined as the first day that the treatment is resumed.

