#### **5.1.2. Duration of Treatment**

Subjects will receive study drug until PD or unacceptable toxicity develops. The continuation of lenalidomide treatment duration until disease progression is supported by Chanan-Khan and Ferrajoli studies which report that subjects with relapsed CLL that have received lenalidomide therapy for more than one year continue to improve their response to treatment (Chanan-Khan, 2006a) (Chanan Khan, 2007) (Ferrajoli, 2008). In the Chanan-Khan study the median time to best response was 5.9 months (range 1.6 to 18.3 months). In the Ferrajoli study time to best response was 6 months in 11 subjects and 9 months in 3 subjects.

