#### 5.1.4. Efficacy

Tumor response will be assessed according to the iwCLL guidelines for the diagnosis and treatment of CLL (Hallek, 2008), including complete response (CR), CR with incomplete bone marrow recovery (CRi), nodular partial response (nPR), partial response (PR), stable disease (SD), and PD. Evaluation of response will be performed after 3 cycles of therapy and every 4 weeks thereafter.

For those subjects who reach PR, CRi or CR, a CT scan of the neck, chest, abdomen and pelvis to assess lymphadenopathies will be performed at the PR and CR/CRi confirmation visits ( $\geq 8$  weeks to  $\leq 12$  weeks after all clinical and laboratory response criteria have been met for PR or CR/CRi). Those subjects whose response was down-graded based on the CT scan interpretation at the PR or CR/CRi confirmation visit will have the CT scan repeated 4 months later at the location where remaining disease has been documented, as long as clinical and laboratory response remains present to try to document further improvement.

For those subjects who reach CR or CRi, a bone marrow aspirate and bone marrow biopsy will be performed at the CR/CRi confirmation visit ( $\geq 8$  weeks to  $\leq 12$  weeks after all clinical and laboratory response criteria have been met). If the bone marrow is hypocellular, a repeat specimen should be obtained after 4 weeks, provided that the blood counts have recovered. If the bone marrow biopsy shows disease involvement (30% or greater lymphocytes, or nodules positive for B-CLL cells by immunohistochemistry), an additional bone marrow biopsy and aspirate will be taken 4 months later as long as clinical and laboratory response remain to document further improvement.

Minimal residual disease (MRD) will be evaluated for those subjects who reach CR or CRi. A peripheral blood and bone marrow aspirate sample will be collected for MRD analysis by flow cytometry at the CR/CRi confirmation visit.

- If peripheral blood and bone marrow are both MRD-positive, peripheral blood samples will be repeated and assessed up to 3 additional times at 8 week intervals to try to document MRD negativity in subjects who reach confirmed CR or CRi (see Follow-up MRD assessments).
- If peripheral blood is MRD-negative and bone marrow is MRD-positive, both peripheral blood and bone marrow should be retested for MRD negativity after  $\geq 12$  weeks. If this repeat bone marrow is MRD-positive, no further testing for MRD will be performed.

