### Response

Response, including evaluation of minimal residual disease (MRD), will be assessed by iwCLL guidelines for diagnosis and treatment of CLL (Hallek, 2008). The response rate based on the best response during the treatment period and the relative proportions in each response category will be examined. Distributions of the responses into the response categories (CR, CRi, nPR, PR, SD, PD) will be provided for each treatment arm. Response rates (CR+CRi+nPR+PR) together with confidence intervals will be provided for each regimen, both for the entire population and for the subgroups defined by the stratification factors.

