### Progression-free Survival (PFS)

Progression-free survival is calculated as the time from randomization to the first documented progression or death due to any cause during or after the treatment period, whichever occurs first. The progression date will be assigned to the earliest time when any progression is observed without prior missing assessments. If withdrawal of consent or loss to follow-up occurs before documented progression or death, then these observations will be censored at the date when the last complete tumor assessments determined a lack of progression.

For subjects who do not develop progressive disease at the time of analysis, if the response from the last visit was 'not evaluable', the most prior visit date with complete evaluation indicating no progressive disease will be used as the censor date.

For subjects who received other anti-CLL or anti-neoplastic therapy before PD, the most prior visit date with complete evaluation indicating no progressive disease will be used as the censor date.

If a subject has 2 or more consecutive missing response assessments followed by PD, the prior assessment date with complete evaluation indicating no progressive disease will be used as the censor date.

If a subject died without PD while in study but there are 2 or more consecutive missing response assessments before death date, the prior assessment date with complete evaluation indicating no progressive disease will be used as the censor date.

Kaplan-Meier product limit methods will be used to estimate the survival functions for treatment arm. Median PFS along with two-sided 95% CIs will be estimated.

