### 13.4. Subgroup Analysis

In addition to analyses that include all subjects, analyses will be performed to compare treatments within the following stratification subgroups:

- Relapsed vs. refractory to their last purine-analog or bendamustine based treatment regimen [relapsed/refractory as defined per the iwCLL guidelines for diagnosis and treatment of CLL (Hallek, 2008)]. If a subject has received both, the status post most recent purine-analog or bendamustine treatment regimen will be used for stratification.
- Age < 65 years of age vs.  $\geq$  65 years of age

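### The optional efficacy subgroup by treatment duration is defined after randomization, partly by progression and death, and its two categories overlap at Cycle 4 Day 1

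*SAP*

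**What the plan says.** The introductory text of SAP section 11 (Efficacy Analysis) adds to the ITT efficacy analyses: "Subgroup analysis might be done by duration of treatment (completed 3 cycles vs. withdraw treatment by Cycle 4 Day 1"). It does not say whether completers are to be set against withdrawers, or arms compared within each group. It names no time origin, tie-break, test or output.

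The other named efficacy subgroups are fixed at randomization. SAP section 13.4 states that "analyses will be performed to compare treatments within the following stratification subgroups", meaning relapsed versus refractory disease and age.

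Four further rules bear on the split:

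- **Treatment ends at progression.** SAP 5.1.2: "Subjects will receive study drug until PD or unacceptable toxicity develops". SAP section 7 lists disease progression and death among the reasons for ending treatment.
- **The same events are endpoints.** SAP section 11: "Progression-free survival is calculated as the time from randomization to the first documented progression or death due to any cause". PD is also the TTP event, and death the OS event.
- **Response is first evaluated at about the cut point.** SAP 5.1.4: "Evaluation of response will be performed after 3 cycles of therapy and every 4 weeks thereafter". The response endpoint is "The response rate based on the best response during the treatment period".
- **Cycle dates can move.** SAP section 9 ends a cycle the day before the next one starts, or 27 days after its own start if none follows. Under Protocol 10.2.3, after a delay, "Day 1 of the next cycle will be defined as the first day that the treatment is resumed".

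**The concern.** A subgroup should be defined by something known at the time origin. Here early PD or death places a subject in the withdrawn group and also counts as that subject's event, so completers are free of such events for about 12 weeks by definition. A gap between the groups could then be read as an effect of staying on drug.

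The labels also overlap. With no delays, cycle 3 ends on day 84 and Cycle 4 Day 1 is day 85. A subject who takes cycle 3 to its end and stops on day 85 has completed 3 cycles and has also withdrawn by Cycle 4 Day 1. The first scheduled response evaluation falls at that visit, so stopping there for PD is foreseeable. Two programmers could assign such subjects differently and both follow the SAP.

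**Working it through.** The SAP attaches no figure to this sentence, so there is nothing of its own to reproduce. The calculation below shows only the scale of the artefact for PFS; TTP and OS were not computed.

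**Inputs.** Protocol 5.3.2.3 (predecessor study): median PFS 5.5 months, 12 months for responders; median treatment duration 3.1 months; reasons for stopping PD 37%, AE 29%, consent withdrawal 15%, death 4%, other 10%. Protocol 5.3.2.1: median PFS 19.4 months in another relapsed/refractory study. SAP 6.5.3: 30.4 days per month. SAP section 3: 104 subjects enrolled. Treatment medians of 8 and 12 months are my assumption.

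**Model.** PFS time P and non-PD stopping time W are independent exponentials. There is no effect of time on drug, and subjects who stop for other reasons are followed.

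- Cut: t0 = 84/30.4 = 2.763 months.
- Rates: λP = ln 2 / (PFS median); λT = ln 2 / (treatment median); λW = λT − λP.
- Withdrawn if min(P, W) < t0.
- PD or death by day 84 at median 5.5: 1 − 2^(−2.763/5.5) = 29%.
- Off treatment by day 84 at median 3.1: 1 − 2^(−2.763/3.1) = 46%.

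**Tie-break.** Let f be the share of on-treatment PFS events before day 84 that are first documented at Cycle 4 Day 1 and counted as completers. The table gives the Cox hazard ratio, completers versus withdrawn, from 400,000 or more simulated subjects per case (error about 0.01, Breslow ties).

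| PFS / treatment median (months) | Follow-up | f = 0 | f = 0.5 | f = 0.9 | f = 1 |
|---|---|---|---|---|---|
| 5.5 / 3.1 | complete | 0.43 | 0.63 | 0.96 | 1.11 |
| 7.18 / 3.1 | complete | 0.54 | 0.74 | 1.02 | 1.10 |
| 12 / 3.1 | 24 months | 0.62 | 0.82 | 1.05 | 1.13 |
| 12 / 8 | 24 months | 0.28 | 0.44 | 0.84 | 1.09 |
| 19.4 / 3.1 | 24 months | 0.69 | 0.86 | 1.05 | 1.11 |
| 19.4 / 8 | 24 months | 0.42 | 0.62 | 0.95 | 1.07 |
| 19.4 / 12 | 24 months | 0.26 | 0.42 | 0.81 | 1.08 |

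In the first row, medians for withdrawn versus completers are 2.1 versus 8.3 months at f = 0 and 2.8 versus 6.6 at f = 0.5. With Efron ties, f = 1 gives about 1.16 instead of 1.11.

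The second row corrects a misfit. The 5.5/3.1 model makes 3.1/5.5 = 56% of stops PD or death, whereas the predecessor reports (37 + 4)/95 = 43%. Matching 43% requires a PFS median of 3.1/0.432 = 7.18 months.

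**What f could be.** Table 2, footnote f, of the Protocol says: "Physical examination of the lymph nodes, spleen and liver will be performed at screening, Study Day 1 and every 28 days thereafter". If PD is found only on that 28-day grid, about 27% of early PD lands on Cycle 4 Day 1, and the 5.5/3.1 hazard ratio is 0.54 with those subjects counted as completers or 0.45 as withdrawn. If PD is instead first called at the evaluation after 3 cycles, nearly all early PD lands there. Deaths cannot be moved in this way; in the predecessor PD was 37/41 = 90% of PD-or-death stops, so f = 0.9 is a reasonable ceiling there.

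**Arms within completers.** With no arm effect on PFS and equal non-PD stopping, the hazard ratio is 1.00. With an assumed 15% versus 45% stopping it remains 1.00 if stopping is unrelated to prognosis. It becomes 0.88 if the two share a gamma frailty of variance 0.5. Neither the imbalance nor the frailty comes from the documents.

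**The case against.** The strongest reply is that comparing completers with withdrawers is not what the SAP intends. Section 11 summarises by arm, and section 13.4 compares treatments within subgroups. Arms within a duration group is at least as natural a reading, and there the calculation shows no bias when early stopping is equal. This stands. It leaves a comparison that randomization does not protect, but not one shown to be biased.

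Three stronger readings are tempting, and the documents do not support them:

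- **That the split always favours completers.** It usually does, but the last two columns show the gap vanishing or reversing when most early PD is documented at Cycle 4 Day 1 and counted with completers.
- **That withdrawn subjects cannot be responders.** One might argue that a response held 8 weeks by day 84 must begin by day 28. That assumes confirmation on drug. Protocol 14.1 continues 28-day response visits after stopping for reasons other than PD or consent withdrawal, and the SAP does not require confirmation by that date. Few responders are likely, because the first scheduled evaluation falls at the cut; none is not established.
- **That interrupted subjects cannot be classified.** Treatment termination is recorded on the CRF (SAP section 7), so a subject on hold without a termination record has not withdrawn. The moving Day 1 only makes the cut date differ between subjects.

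It is also fair that the sentence is permissive and that the hazard ratios rest on borrowed or assumed medians.

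**Conclusion.** The point holds and is minor. The split is set after randomization, depends partly on endpoint events, and has an unresolved overlap at Cycle 4 Day 1. Compared from randomization, the two groups can differ in PFS with no effect of time on drug. In the illustrations the hazard ratio runs from 0.26 to 0.86 when none to half of the early events are counted with completers, and reaches about 1.1 to 1.2 when all are. These figures assume exponential times, independent non-PD stopping and medians from other studies; they show scale and do not predict this trial.

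The analysis is optional and secondary, and has no test attached. The ITT efficacy analyses and the primary safety endpoint are untouched.

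**What to change.** Delete the sentence. If the sponsor wants the question addressed, replace it with a landmark analysis labelled descriptive and non-randomized:

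- Use one fixed time from randomization, late enough to include the first scheduled response evaluation: Cycle 4 Day 1 (day 85 from first dose), plus the 3-day visit window (day 88), plus an allowance for the gap from randomization to first dose. The documents do not give that gap, so the sponsor should set it. Day 84 from randomization would be too early.
- Include only subjects alive and without adjudicated PD by then.
- Classify as off drug only those with a recorded permanent treatment termination by that date; interrupted subjects count as on drug.
- Time PFS and OS from the landmark.
- Make no response-rate comparison with the off-drug group.

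The cost is one SAP sentence, no new data, and a smaller set. At day 84, 104 × 2^(−2.763/m) gives 73, 80, 89 and 94 subjects for PFS medians m of 5.5, 7.18, 12 and 19.4 months; at day 88 (2.895 months) it gives 72, 79, 88 and 94. The landmark removes the built-in artefact, but prognostic differences between subjects on and off drug remain.
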